5.2. Exclusion Criteria

Participants are excluded from the study if any of the following criteria apply:

NO	STANDARD EXCLUSION CRITERIA
Participants who meet any of the following exclusion criteria will not be included in the study.	
Medical History	
1	
History of, or currently active, symptoms or signs suggestive of upper or lower respiratory tract infection within 4 weeks prior to the first study visit.
 
a) Any history or evidence of any other clinically significant or currently active systemic comorbidities including psychiatric disorders (includes participants with a history of depression and/or anxiety).
 
b) And/or other major disease that, in the opinion of the Investigator, may put the participant at undue risk, or interfere with a participant completing the study and necessary investigations (e.g autoimmune disease or immunodeficiency).

2	
Guidance
 
The following conditions apply:
 
 Participants with clinically mild atopic eczema/atopic dermatitis and clinically mild psoriasis may be included at the Investigator's discretion (e.g., if small amounts of regular topical steroids are used, no eczema in cubital fossa; moderate to large amounts of daily dermal corticosteroids is an exclusion). Any rhinitis (specifically upper respiratory tract symptoms related to hay fever) which is clinically active or history of moderate to severe rhinitis, or history of seasonal allergic rhinitis likely to be active at the time of inclusion into the study and/or requiring regular nasal corticosteroids on an at least weekly basis, within 30 days of admission to quarantine will be excluded. Participants with a history of currently inactive rhinitis (within the last 30 days) or mild rhinitis may be included at the PI's discretion. Participants with a physician diagnosed underactive thyroid who have been controlled on treatment for at least 6 months with evidence of a normal thyroid function test (TFT) can be included at the discretion of the PI. Any concurrent serious illness including history of malignancy that may interfere with the aims of the study or a participant completing the study. Basal cell carcinoma within 5 years of initial diagnosis or with evidence of recurrence is also an exclusion. Participants with a history of psychiatric illness including depression and/or anxiety of any severity within the last 2 years can be included if the Patient Health Questionnaire (PHQ-9) and / or the Generalised Anxiety Disorder Questionnaire (GAD-7) is less than or equal to 4. Participants with a PHQ-9 or GAD-7 score of between 5 and 9 may be included following consultation with a Senior Physician (Clinical Lead for Screening) who may advise further consultation with the PI.

NO	STANDARD EXCLUSION CRITERIA
Participants who meet any of the following exclusion criteria will not be included in the study.	
	
 • Participants reporting physician diagnosed migraine can be included provided there are no associated neurological symptoms such as hemiplegia or visual loss. Cluster headache/migraine or prophylactic treatment for migraine is an exclusion. • Participants with physician diagnosed mild Irritable Bowel Syndrome (IBS) not requiring regular treatment can be included at the discretion of the PI.
3	Participants who have smoked \geq 10 pack years at any time [10 pack years is equivalent to one pack of 20 cigarettes a day for 10 years].
4	A total body weight \leq 50 kg and Body Mass Index (BMI) \leq 18 kg/m ² and \geq 30kg/m ² .
5	Females who: 
 Are breastfeeding, or Have been pregnant within 6 months prior to the study.
6	History of anaphylaxis-and/or a history of severe allergic reaction or significant intolerance to any food or drug or vaccine, including hypersensitivity to any of the constituents of the study vaccine, as assessed by the PI.
7	Venous access deemed inadequate for the phlebotomy and cannulation demands of the study.
8	
 Any significant abnormality altering the anatomy of the nose in a substantial way or nasopharynx that may interfere with the aims of the study and in particular any of the nasal assessments or viral challenge, (historical nasal polyps can be included, but large nasal polyps causing current and significant symptoms and/or requiring regular treatments in the last month will be excluded). Any clinically significant history of epistaxis (large nosebleeds) within the last 3 months of the first study visit and/or history of being hospitalized due to epistaxis on any previous occasion. Any nasal or sinus surgery within 3 months of the first study visit.
Prior or Concomitant Medications and Assessments	
9	
 Evidence of vaccinations with licensed live attenuated vaccines within the 4 weeks prior to the planned date of viral challenge/first dosing with IMP (whichever occurs first). Evidence of vaccinations with licensed vaccines which are not live attenuated within the 2 weeks prior to the planned date of viral challenge/first dosing with IMP (whichever occurs first). Intention to receive any vaccination(s) before at least 28 days after the viral challenge (NB. No travel restrictions will apply after the Day 28 Follow-up visit).
10	Receipt of blood or blood products, or loss (including blood donations) of 550 mL or more of blood during the 2 months prior to the planned date of viral challenge/first dosing with IMP (whichever occurs first) or planned during the 2 months after the viral challenge.
11	
 Receipt of any investigational drug within 3 months prior to the planned date of viral challenge/first dosing with IMP (whichever occurs first).

NO	STANDARD EXCLUSION CRITERIA
Participants who meet any of the following exclusion criteria will not be included in the study.	
	
 b) Previous vaccination with any licensed or investigational RSV vaccine before enrolment into the study. c) Receipt of three or more investigational drugs within the previous 12 months prior to the planned date of viral challenge/first dosing with IMP (whichever occurs first). d) Prior inoculation with a virus from the same virus-family as the challenge virus. e) Prior participation in another human viral challenge study with a respiratory virus in the preceding 3 months, taken from the date of viral challenge in the previous study to the date of expected viral challenge in this study. f) Receipt of treatment with immunosuppressive therapy.
12	
 a) Confirmed positive test for drugs of abuse and cotinine on first study visit. One repeat test allowed at PI discretion. b) History or presence of alcohol addiction, or excessive use of alcohol (weekly intake in excess of 28 units alcohol; 1 unit being a half glass of beer, a small glass of wine or a measure of spirits), or excessive consumption of xanthine containing substances (e.g. daily intake in excess of 5 cups of caffeinated drinks e.g. coffee, tea, cola).
13	A forced expiratory volume in 1 second (FEV1) < 80%.
14	Positive human immunodeficiency virus (HIV), active hepatitis A (HAV), B (HBV), or C (HCV) test.
Other	
15	Those employed or immediate relatives of those employed at hVIVO, Pfizer or any vendor.
16	Any other finding that, in the opinion of the Investigator, deems the Participant unsuitable for the study.

5.3. Lifestyle Considerations

5.3.1. Meals and Dietary Restrictions

No dietary restrictions are required before or after dose administration.

Participants must not consume any food containing poppy seeds or any codeine containing formulation starting 72 hours before screening, before vaccination and before admission to the quarantine Unit (in order to avoid false-positive urine drug screen).

5.3.2. Caffeine, Alcohol, and Tobacco

Participants must abstain from ingesting caffeine- or xanthine-containing products (e.g., coffee, tea, cola drinks, and chocolate) for 48 hours prior and during quarantine and for 48 hours prior to all visits requiring spirometry.

Participants must not consume alcohol for 72 hours prior and during quarantine and for 72 hours prior to any clinic visits.

Participants must not smoke or use tobacco or nicotine containing products for 72 hours prior to and during quarantine. Participants that are current smokers may be continued in the study if, in the opinion of the PI, cessation of smoking during quarantine will not lead to withdrawal symptoms which could interfere with the accurate recording on the Symptoms Diary Card.

5.3.3. Activity

Participants must refrain from strenuous exercise for 48 hours prior and during quarantine and for 48 hours prior to each clinic visit (unless it is within the usual activity of the participant) in order to avoid potential spurious elevation of clinical laboratory safety parameters.

5.4. Screen Failures

Screen failures are defined as participants who sign the study-specific Informed Consent Form (ICF) but are not subsequently randomised to receive study intervention (i.e. vaccination).

If an individual does not meet the criteria for participation in this study (screen failure) and the Investigator would like to re-screen the participant, and they are still within the allowed screening window (Day -118 to Day -29), then only the assessments for which the participant failed must be re-assessed.

If an individual does not meet the criteria for participation in this study (screen failure) and the Investigator would like to re-screen the participant at a later time (i.e. outside of the allowed screening window), then full re-screening must be completed.

6. Study Intervention

Study interventions administered to participants are described in Table 1.

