Summary of study design	
This is an exploratory proof-of-concept randomised, Phase 2a, double-blind, placebo-controlled study to evaluate the safety, immunogenicity and efficacy of an RSV vaccine against RSV-A Memphis 37b infection in healthy subjects.
 
The study is divided into the following study phases:
 
Screening:
 
 Screening prior to vaccination from Day -84 to Day -29 (Day -118 for RSV serology). Pre-screening data collected through the hVIVO generic screening process prior to signing the study specific consent form, and prior to vaccination from Day -84 to Day -29 (Day -118 for RSV serology), may be transferred to this study after study-specific consent form has been signed by the participant. Pre-screening data obtained prior to this window can be re-assessed any time prior to vaccination from Day -84 to Day -29. 
Vaccination & follow up visits:
 
 Vaccination on Day -28 (± 3 days), participants will be randomised 1:1 to receive RSVpreF or placebo Follow up clinic visit 1 day post vaccination Follow up clinic visit 7 days post vaccination (± 1 day) 
Quarantine & virus challenge:
 
 Admission to the Quarantine Unit on Day -2/-1; resident in the Quarantine Unit for approximately 15 days, from admission on Day -2 to planned discharge on Day +12. Challenge with Challenge Virus on Day 0. Discharge from quarantine planned on Day +12 
Follow-Up Clinic visits:
 
 Day +28 (± 3 days). Day +155 (± 14 days)
Expected duration of subject participation	Approximately 6 months from randomisation to the subject's last scheduled visit.
Overall duration of clinical phase	The length of the clinical phase is expected to be 9 months from start of vaccination for the first participant (FPFV) to the last scheduled study visit for the last participant (LPLV).
End of study	The end of the study will be considered as the last visit of the last participant in the study.

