Safety Assessments																									
Solicited AE recording (k)	X	←	→																						
Unsolicited AE recording (l)		←	→																						
Medically Attended AEs (MAEs) and SAE recording		←	→																						
Concomitant medications	X	←	→																						

KEY NOTES FOR SCHEDULE OF EVENTS

hVIVO template identifier: (G_0687) v3.0

X	Once
BD	Twice Daily, 12 hours between assessments (\pm 1 hour).
TDS	Three Times Daily, at the same time each day (\pm 1 hour).
T	To determine tolerance of the procedure only (sample will not be tested).
*	All screening assessments will be performed under hVIVO Generic Screening process. Results of tests or examinations performed under hVIVO Generic Screening process, and from Day -118 (Day -118 for viral serology and Day-84 for other assessments including safety laboratory test) prior to vaccination may be used to determine eligibility without the need to repeat the assessment following study specific consent.
+	Only the applicable Inclusion/Exclusion criteria will be reviewed at each time point.
#	Admission can occur on Day -2 or Day -1 and therefore procedures can be performed on Day-2 or Day-1. If admission is on Day -1 then those procedures which occur on both Day -2 and -1 will only be captured using the timepoints of Day -1. For TDS assessments on Day -2/Day-1: When Quarantine Admission occurs on Day -1, assessments will be performed up to three times daily.
a	Study-specific consent may occur on the day of vaccination, providing all required eligibility information has been collected through the hVIVO generic screening process.
b	Height will be taken at Screening only.
c	Distribution of paper tissues and bags will start on Day -1, with the first collection on Day 0. Thereafter collection of tissues will occur at the same timepoints (\pm 1 hour) with tissues distributed 24h ahead.
d	Assessments will be performed at the same time each day during quarantine (\pm 1 hour).
e	Blood will be drawn under non-fasted conditions. Repeat bloods may be drawn under fasted conditions if a lipid profile (triglyceride) or glucose is required (at PI discretion).
f	Vaccine and viral challenge serology (e.g. RSV neutralisation antibody assay) will be performed to determine eligibility and seroconversion. Non-vaccine antigen-binding antibody assay will be used for serological detection/seroconversion of community acquired RSV infection between vaccination and viral challenge.

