4.1. Overall Design

This is a randomised, Phase 2a, double blind, placebo-controlled study to evaluate the safety, immunogenicity and efficacy of an RSV vaccine against RSV-A Memphis 37b infection in healthy participants.

The total duration of study participation for a participant is approximately 6 months after vaccination, with the following sequence and duration of study periods:

Screening Phase:

- Screening prior to vaccination from Day -84 to Day -29 (Day -118 for RSV serology) Pre-screening data collected through the hVIVO generic screening process prior to signing the study specific consent form, and prior to vaccination from Day -84 to Day -29 (Day -118 for RSV serology) may be transferred to this study after study-specific consent form has been signed by the participant. Pre-screening data obtained prior to this window can be re-assessed any time prior to vaccination from Day -84 to Day -29.

Vaccination Phase:

- Vaccination on Day -28 (± 3 days), participants will be randomised 1:1 to receive RSVpreF or placebo
- Follow up clinic visit 1 day post vaccination
- Follow up clinic visit 7 days post vaccination (± 1 day)

Quarantine Phase:

- Admission to the Quarantine Unit on Day -2/-1; resident in the Quarantine Unit for approximately 15 days, from admission on Day -2 to planned discharge on Day +12.
- Challenge with Challenge Virus on Day 0.
- Discharge from quarantine planned on Day +12

Follow-Up Phase:

- Day +28 (± 3 days).
- Day +155 (± 14 days)

Participants will be pre-screened for susceptibility to RSV infection, i.e., have levels of RSV neutralising antibodies compatible with susceptibility to RSV infection.

Participants will be randomised to receive a single intramuscular dose of RSVpreF or Placebo on Day -28 (± 3 days):

- **Reference article product**
 - PF-06928316 also known as RSVpreF
 - Dose: 120mcg

- **Placebo product**

- Placebo to match vaccine

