4	
A severe non-serious adverse reaction (i.e. severe non-serious adverse events considered at least possibly related to the IMP administration) is reported in two participants, independent of whether or not within the same system-organ/class.
	
If such a status occurs at any point during the study, then further administration of RSVpref will not take place. The PI and the SMM will review the data and make decisions on whether it is appropriate to recommence dosing (via a substantial amendment, if indicated) or terminate the study.
 
Regulatory authority approval via a substantial amendment would be required in order to recommence the study.

In any event, participant follow-up should continue until resolution or stabilisation of AEs and final follow-up on Day +155 (\pm 14 days).

8. Study Assessments and Procedures

Unless otherwise stated, study assessments will be performed according to hVIVO SOPs.

Study procedures and their timing are summarised in the SoA. Protocol waivers or exemptions are not allowed. Adherence to the study design requirements, including those specified in the SoA, is essential and required for study conduct. Immediate safety concerns should be discussed with the Sponsor upon occurrence or awareness to determine if the participant should continue or discontinue study intervention

All screening evaluations must be completed and reviewed to confirm that potential participants meet all eligibility criteria. The investigator will maintain a screening log to record details of all participants screened and to document eligibility or record the reasons for screening failure, as applicable.

For all study assessments, the value obtained nearest to dosing will be used as the baseline measure for assessments, unless stated otherwise.

Procedures conducted as part of the hVIVO Generic Screening process and obtained before signing of the study specific Informed Consent Form (ICF) may be utilised for screening or baseline purposes provided the procedures met the protocol-specified criteria and were performed within the time frame defined in the SoA.

Where applicable, unless otherwise stated, normal ranges will be identified in the Investigator Trial Master File (TMF).

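### Section 5.4 applies the RSV-serology limit of Day -118 to all re-screening assessments, in conflict with the Day -84 limit set for non-serology tests elsewhere

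*Combined protocol and SAP*

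**What the plan says.** Section 5.4 covers people who signed the study-specific consent form but were not randomised. It states one window for all assessments: if "they are still within the allowed screening window (Day -118 to Day -29), then only the assessments for which the participant failed must be re-assessed". Complete re-screening is required only later, when the person is "outside of the allowed screening window), then full re-screening must be completed".

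Three other places split the window by type of assessment:

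- Synopsis (1.1): "Screening prior to vaccination from Day -84 to Day -29 (Day -118 for RSV serology"; section 4.1 gives the same limits.
- SoA key note marked with an asterisk (1.3): "Day -118 for viral serology and Day-84 for other assessments including safety laboratory test".
- Section 4.1, on older data: "Pre-screening data obtained prior to this window can be re-assessed any time prior to vaccination from Day -84 to Day -29".

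The opening text of section 8 lets procedures done under generic screening, before study consent, be used "provided the procedures met the protocol-specified criteria and were performed within the time frame defined in the SoA".

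Section 7.2.1 postpones dosing for people who are ineligible for a transient reason at the first study visit, re-invites them to a later quarantine group, and refers to section 5.4 for re-screening.

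**The concern.** Day -118 is the serology limit, and section 5.4 presents it as the limit for everything. Within that window it asks for a repeat of the failed items only. A non-serology result dated between Day -118 and Day -85 is therefore out of date under the SoA, yet need not be repeated under section 5.4.

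What is at stake is the evidence for eligibility at vaccination. Inclusion 3 (good health, judged partly on ECG and routine laboratory tests), exclusion 13 (FEV1) and exclusion 14 (HIV and hepatitis) could rest on results that the SoA treats as expired. There is also a question of classification. Sections 5 and 8 do not permit waivers, and the Per Protocol set excludes major deviations. The same participant could look compliant under one section and deviating under another.

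**Working it through.** **Inputs**

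- Limit for all assessments in section 5.4: Day -118.
- Limit for non-serology assessments in the SoA key note, synopsis and section 4.1: Day -84.
- End of the window in all of them: Day -29.
- Vaccination: "Vaccination on Day -28", plus or minus 3 days (section 4.1), so Day -31 to Day -25.

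The protocol does not state the gap itself; it follows from these days.

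**Gap between the limits:** 118 - 84 = 34 days.

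**Oldest non-serology result at vaccination** (vaccination day minus test day):

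| Vaccination day | SoA limit (Day -84) | Section 5.4 read literally (Day -118) | Excess |
|---|---|---|---|
| -31 | 84 - 31 = 53 days | 118 - 31 = 87 days | 34 |
| -28 | 84 - 28 = 56 days | 118 - 28 = 90 days | 34 |
| -25 | 84 - 25 = 59 days | 118 - 25 = 93 days | 34 |

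At Day -28 the ratio is 90/56 = 1.61. These are maxima; a result dated between Day -118 and Day -85 exceeds the SoA limit by 1 to 34 days.

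**How a participant could get there.** Take someone who signs the consent form at the vaccination visit, is found transiently ineligible, and is deferred under section 7.2.1. Day 0 moves, so every earlier test ages. As an illustration (assumed figures), tests taken on Day -60 become Day -60 - 35 = Day -95 if the new quarantine group is five weeks later. Non-serology results are then 95 - 84 = 11 days past the SoA limit but inside the section 5.4 window, where only the failed item must be repeated.

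**What the vaccination visit covers.** As far as the SoA table can be read:

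- Done again: eligibility review, medical and medication history, complete physical examination, vital signs, urinalysis and urine pregnancy test.
- Optional: biochemistry and coagulation.
- No entry: haematology, cardiac enzymes, ECG, spirometry, HIV/hepatitis. The first four next appear at quarantine admission, after vaccination. HIV/hepatitis appears at screening only.

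**The case against.** The strongest reply is that the Day -84 limit never stops applying. The SoA says that all screening assessments run under the generic process, and section 8 accepts generic-screening results only within the SoA time frame, calls SoA adherence essential and forbids waivers. On this view section 5.4 says which tests must be redone because they were failed; it does not make expired results valid. The SoA key note itself opens with Day -118 as the outer bound before splitting it, so section 5.4 may simply have dropped the split. Section 4.1 also provides for re-assessing older data.

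Much of this stands. A site that follows the SoA would not use the older tests. A reader might infer that the protocol authorises vaccination on expired safety tests; section 8 does not support that. A reader might also infer that every screen failure first tested between Day -118 and Day -85 is affected. That is too wide: section 5.4 applies only after study-specific consent, which section 10.1.3 places at the vaccination visit when generic-screening data are used. Nor is it right that nothing is checked before dosing, given the list above and the PI's freedom to add safety assessments. Finally, loss before challenge is possible but not automatic: discontinuation for a laboratory finding requires clinical significance that precludes participation (7.2), and replacement is optional (7.4).

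The reply does not remove the conflict. Section 5.4 has its own numerical window, says that only failed items need repeating, and reserves full re-screening for people outside that window. Section 7.2.1 sends deferred participants there, and no text says which rule prevails.

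**Conclusion.** The inconsistency is real. Section 5.4 conflicts with the synopsis, section 4.1 and the SoA key note. Read literally, it permits non-serology results up to 34 days older than the SoA limit: up to 90 against 56 days at a Day -28 vaccination, or 87 to 93 against 53 to 59 across the vaccination window. Because section 8 keeps the SoA time frame in force, the finding is two competing rules with no stated precedence, rather than a clear relaxation of the limit.

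The exposure is mainly haematology, cardiac enzymes, ECG, spirometry and HIV/hepatitis, plus biochemistry and coagulation where the optional vaccination-visit tests are not done. That list depends on an SoA table that came through text extraction damaged. The protocol gives no number of re-screened participants; few are likely to be concerned. The point bears on eligibility and safety data. Sample size, power and type I error are not affected.

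**What to change.** Reconcile section 5.4 with the synopsis, section 4.1, the SoA key note and the opening of section 8. In practice, replace the single window in section 5.4 with a reference to the SoA's per-assessment windows, and state that on re-screening any assessment outside its own SoA window is repeated along with the failed one. Section 7.2.1 refers to an allowed time window without defining it and could point to the same text.

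This review takes no view on how long any window ought to be; the request is that all sections give the same one. If the sponsor did intend a longer limit for re-screened participants, the SoA and section 8 would have to say so.

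The cost is one sentence in the next amendment, plus repeat routine tests for the few people whose results have passed the SoA limit.
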